#### 5.0 RANDOMIZATION/RECRUITMENT DETAILS (If applicable)

- Randomization groups, how will subjects be randomized:

All subjects who are patients of Drs. [name] and/or [name] and scheduled for kidney stone-related surgery will be potentially recruited.

Part 1: In an initial open run-in period, six patients will be recruited and given a dose of 10 mg baclofen preoperatively so that potential side effects can be assessed in an unblinded fashion.

Part 2: After that, patients will be identified and initially stratified into two groups based on preoperative opioid use. If daily using >30 Oral Morphine Equivalents (OMEs) for more than one month they will be designated as Opioid Tolerant. Otherwise, they will be included in the Opioid Naïve group. These two groups will then be each randomized (envelope assignment) into receiving either baclofen (10 mg, p.o. x 1) or placebo as a preoperative medication such that there will be 4 groups of 20 patients identified:

Group 1: Opioid Tolerant – baclofen

Group 2: Opioid Tolerant – placebo

Group 3: Opioid Naïve – baclofen

Group 4: Opioid Naïve - placebo

- Blinded  Yes  No (Single  Double  please check box).

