## 1.0 SUMMARY OF STUDY

The present study proposes to study the effect of a single preoperative dose of baclofen on pain treated in the first 24 hours after kidney stone-related surgeries using a placebo-controlled, double-blind methodology. Because this patient population often has a history of significant opioid use, which would be expected to alter postoperative pain medication requirements, patients will be stratified into those which would be expected to be opioid tolerant (use >30 OME daily) and those who are generally opioid naïve.

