### **3.0 OBJECTIVE(S) & HYPOTHESIS**

Purpose of study:

To determine whether a single, oral dose of baclofen alters postoperative opioid requirements

Study Hypothesis:

We hypothesized that a single, oral dose of baclofen given to patients undergoing kidney stone surgery will reduce postoperative opioid requirements measured in the PACU and in the first 24 hours following surgery.

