#### 6.0 STUDY INTERVENTIONS/PROCEDURES

- Study design: Placebo-controlled double-blind
- Comparison groups (for prospective and clinical trials only).

Placebo treated individuals

- Timeline of interventions (for prospective and clinical trials only).

Patients will be recruited preoperatively by Drs. [name] and [name], in addition to anesthesiology-related personnel in the KPAC. Informed consent will be obtained at that time. On the Day of Surgery, subjects will be contacted by study personnel in the Preoperative Holding area to confirm patient participation and then a randomization envelope containing a single dose of either baclofen or placebo will be opened (Groups 1&2 intermixed; Groups 3&4 intermixed; envelopes will be prepared ahead of time by a different investigator according to a randomization table). Subjects will then consume the pill in the envelope and this will be recorded. Patients will then be treated intraoperatively and postoperatively according to the standard of care associated with these surgeries but with an attempt to utilize consistent doses of intraoperative opioids other agents across groups and standardized PACU orders. After discharge from the

PACU patients' pain will be treated with PCA morphine. Notably, the treating anesthesiologist and all PACU personnel will be blinded to the drug that was administered preoperatively. The total use of analgesics, measures of any other side effects (nausea, excessive sedation) will be recorded for 24 hours.

- **Measured Outcomes:**
  - a. Primary outcomes: Postoperative opioid consumption (measured as OMEs)
  - b. Secondary outcomes: Incidence of nausea/vomiting; excessive sedation per patient self assessment; any other untoward events

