## **9.0 STATISTICAL CONSIDERATIONS**

- Original Plan for Statistical Analysis : Data analysis will be by ANOVA analysis using Tukey's HSD for post-hoc analysis for primary outcome data and Fishers Exact test for categorical incidence data. A mid-point analysis was proposed after the study of 40 subjects.

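### Preoperative opioid dose enters the plan only as a two-level split; adding the numeric dose to a named model in Section 9 is a cheap gain in precision, not the repair of an error

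*Combined protocol and SAP*

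**What the plan says.** Section 1 stratifies on preoperative opioid use because a history of use is something "which would be expected to alter postoperative pain medication requirements". It gives the cut as "patients will be stratified into those which would be expected to be opioid tolerant (use >30 OME daily", with no duration.

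Section 5 adds a duration: "If daily using >30 Oral Morphine Equivalents (OMEs) for more than one month they will be designated as Opioid Tolerant". The rest follow by default: "Otherwise, they will be included in the Opioid" Naive group. Each stratum is randomized to baclofen or placebo, "such that there will be 4 groups of 20 patients identified", so 80 patients in all.

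Section 3 states one directional hypothesis, that baclofen "will reduce postoperative opioid requirements measured in the PACU and in the first 24 hours following surgery". Section 6 defines the outcome as "Primary outcomes: Postoperative opioid consumption (measured as OMEs"). Section 9 gives the analysis in one line: "Data analysis will be by ANOVA analysis using Tukey's HSD for post-hoc analysis for primary outcome data". It names no factor, covariate, interaction, variance assumption or outcome scale. No SD, effect size, alpha or power is given in the documents.

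**The concern.** The plan itself treats prior opioid use as prognostic for the primary outcome, then reduces it to two levels. Neither level is narrow. Tolerant has no upper limit. Naive holds non-users, users of up to 30 OME/day and, on a literal reading of Section 5, users above 30 OME/day for one month or less. If dose predicts consumption within a stratum, that variation is counted as noise. Staff must judge the daily OME in order to stratify, so the information exists at that moment; the documents do not say whether the number is kept.

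A second, smaller matter concerns the post-hoc comparisons. Standard Tukey HSD applies one pooled error variance to all four cells. If heavier users vary more in consumption, that variance is too large for one stratum and too small for the other. At stake are some power for the Section 3 hypothesis and the reliability of any statement about one stratum.

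**Working it through.** **Inputs.** From the documents: four cells of 20 (4 × 20 = 80), outcome in OMEs, ANOVA with Tukey. There is no stated power figure to reproduce. Assumed: two-sided 0.05; log-normal outcome with CV 0.8; placebo means 30 OME (Naive) and 60 OME (Tolerant); 35% reduction in both strata; dose related to outcome in Tolerant only.

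**Step 1, what a covariate can do, by hand.** Placebo SDs are 0.8 × 30 = 24 and 0.8 × 60 = 48; baclofen SDs are 0.65 times these, 15.6 and 31.2. The average effect is (0.35 × 30 + 0.35 × 60)/2 = 15.75 OME. Its variance is ¼ × (24² + 15.6² + 48² + 31.2²)/20 = 51.21, so SE = 7.16 and effect/SE = 2.20. A within-stratum correlation ρ multiplies the two Tolerant terms by 1 − ρ². At ρ = 0.3, 0.5 and 0.7, SE falls to 6.89, 6.40 and 5.58, and effect/SE rises to 2.29, 2.46 and 2.82. Normal power, Φ(effect/SE − 1.99), goes from 58% to 62%, 68% and 80%.

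**Step 2, simulation.** This drops the idealization. Outcomes are skewed, the correlation is set on the latent normal scale (so it is weaker in OMEs), and one slope is fitted across strata. Two independent runs gave overall power, without → with dose:

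| Correlation | Run 1 | Run 2 | Change (points) |
|---|---|---|---|
| 0 | 63.5 → 62.7% | 63.9 → 63.2% | −0.8, −0.7 |
| 0.3 | 63.4 → 65.0% | 63.3 → 64.6% | +1.6, +1.3 |
| 0.5 | 63.4 → 69.7% | 63.7 → 70.0% | +6.3, +6.3 |
| 0.7 | 63.7 → 79.2% | 63.3 → 78.3% | +15.5, +15.0 |

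The type I error of the covariate model is 4.4 to 5.2%. If 10% of Naive patients are above 30 OME/day and the correlation holds in both strata, power moves 63.1 → 62.5% at 0, 63.7 → 65.9% at 0.3 and 64.2 → 72.5% at 0.5.

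**Step 3, outcome scale.** At correlation 0 and with no zero values, a log analysis has 77.5% power against 63.5% in OMEs. With 5% zeros, log(y+1) has 43.9% against 57.8%. The better scale depends on a zero rate that the documents do not give. On the log scale at correlation 0.5 in Tolerant only, one common slope gains almost nothing (77.7 → 77.9%), whereas a slope per stratum reaches 81.8%.

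**Step 4, pooled variance in Tukey.** Let r be the Tolerant:Naive SD ratio, with Naive SD = 1. The pooled SD is √((1 + r²)/2). Tukey's critical value for four groups and 76 df is 3.715/√2 = 2.627. In each stratum's own SE units the hurdle is 2.627 × pooled SD for Naive, and that divided by r for Tolerant. False-positive rates are per comparison, simulated with normal data:

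| r | Pooled SD | Hurdle Naive / Tolerant | False positives Naive / Tolerant |
|---|---|---|---|
| 1 | 1.00 | 2.63 / 2.63 | 1.0% / 1.0% |
| 1.5 | 1.27 | 3.35 / 2.23 | 0.1% / 2.9% |
| 2 | 1.58 | 4.15 / 2.08 | 0.01% / 4.3% |
| 3 | 2.24 | 5.87 / 1.96 | below 0.01% / 5.6% |

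The overall treatment test keeps a level of 5.0 to 5.2% at all four ratios.

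**Step 5, do own variances stop the strata from disagreeing?** No. If the effect is equal in OMEs (1 Naive SD), exactly one stratum is significant in 48, 37 and 20% of trials under Tukey at r = 1.5, 2 and 3, against 55, 65 and 73% with own variances and two contrasts. Part of Tukey's lower figure is low power in both strata. With a 35% reduction in both, CV 0.8 and Tolerant mean twice Naive, the figures are 36% under Tukey and 40% with own variances.

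**The case against.** Stratified randomization already handles prior use in the design, no dose-outcome correlation is documented, and the gain is small below about 0.5. That stands, and is why this is an improvement rather than a fault. Section 9 may also intend a two-way model; it does not say. Even so, a two-way model without dose leaves within-stratum variation in the error term.

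The variance point is purely conditional. No stratum SD is given, and with equal SDs pooling is correct. Own variances would then cost about 2 points of within-stratum power for a 1-SD effect (70% to 68%, six-contrast adjustment kept).

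A reader might infer something stronger: that the plan is likely to report baclofen as working in Tolerant but not in Naive patients when it works in both, and that own variances would prevent this. At r = 2 with a 1-SD effect in each stratum, that pattern does occur in 70% of trials under Tukey against 16%. The documents do not support resting on this. At CV 0.8, 1 SD is an 80% reduction in consumption, and neither that effect nor the SD ratio is documented. With a 35% reduction (CV 0.8, Tolerant mean twice Naive), the pattern occurs in 35% against 20%, and Step 5 shows that total disagreement does not fall. Nor does the plan say that significance will be compared across strata: Section 3 has one hypothesis, and Section 9 labels Tukey as post hoc.

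**Conclusion.** The point holds as a cheap improvement. The plan calls prior opioid use prognostic, keeps only two open-ended categories, and names no model that could use the rest. The expected change in overall power runs from about −1 point if dose is unrelated to outcome, through +1 to 2 and +6, to about +15 at a correlation of 0.7, all on the assumed inputs above. The overall test of the Section 3 hypothesis is not invalid, and the documents do not show that the numeric dose goes unrecorded.

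The variance point is secondary and depends on unequal SDs. At an assumed ratio of 2, Tukey's per-comparison error is about 0.01% in one stratum and 4.3% in the other, against 1.0% in each when SDs are equal. Own variances correct the width of the stratum intervals but do not make split verdicts rarer, so a difference between strata can be claimed only from an interaction estimate.

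**What to change.** 1. Record the numeric preoperative daily OME at stratification.
2. In Section 9, prespecify treatment, opioid stratum and continuous preoperative OME as model terms, with the treatment term as the overall test. Fix the outcome scale before unblinding; if it is a log scale, fit a separate OME slope in each stratum.
3. Estimate baclofen minus placebo in each stratum with that stratum's own error variance, and state how many contrasts the adjustment covers (two within-stratum, or all six).
4. Base any claim that the effect differs by stratum on the treatment-by-stratum interaction: the difference of the two estimates, SE = √(SE₁² + SE₂²), Satterthwaite df, 95% interval. State that its power is low, about 10 to 11% under a 35% reduction in both strata with the Tolerant mean twice the Naive mean, so a non-significant result does not show equal effects.
5. Reconcile the Section 1 and Section 5 definitions of Tolerant, including where users above 30 OME/day for one month or less belong.

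The cost is one data field, SAP wording, one degree of freedom (two with separate slopes) and about 1 point of power if dose is uninformative. If enrolment has begun, doses would have to be recovered, and the documents do not show whether that is possible. Adjusting for two contrasts with own variances brings the chance of any false within-stratum claim to about 5%, against 2.1% under Tukey at equal SDs. It also makes Tolerant intervals 11% narrower than Tukey's at SD ratio 1, but 4, 12 and 19% wider at 1.5, 2 and 3.

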#### 6.0 STUDY INTERVENTIONS/PROCEDURES

- Study design: Placebo-controlled double-blind
- Comparison groups (for prospective and clinical trials only).

Placebo treated individuals

- Timeline of interventions (for prospective and clinical trials only).

Patients will be recruited preoperatively by Drs. [name] and [name], in addition to anesthesiology-related personnel in the KPAC. Informed consent will be obtained at that time. On the Day of Surgery, subjects will be contacted by study personnel in the Preoperative Holding area to confirm patient participation and then a randomization envelope containing a single dose of either baclofen or placebo will be opened (Groups 1&2 intermixed; Groups 3&4 intermixed; envelopes will be prepared ahead of time by a different investigator according to a randomization table). Subjects will then consume the pill in the envelope and this will be recorded. Patients will then be treated intraoperatively and postoperatively according to the standard of care associated with these surgeries but with an attempt to utilize consistent doses of intraoperative opioids other agents across groups and standardized PACU orders. After discharge from the

PACU patients' pain will be treated with PCA morphine. Notably, the treating anesthesiologist and all PACU personnel will be blinded to the drug that was administered preoperatively. The total use of analgesics, measures of any other side effects (nausea, excessive sedation) will be recorded for 24 hours.

- **Measured Outcomes:**
  - a. Primary outcomes: Postoperative opioid consumption (measured as OMEs)
  - b. Secondary outcomes: Incidence of nausea/vomiting; excessive sedation per patient self assessment; any other untoward events

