## 2.0 BACKGROUND & RATIONALE

Postoperative pain continues to be a significant clinical problem. Use of perioperative adjuvants has improved postoperative pain control. The GABA-B receptor agonist, baclofen, is an appropriate drug to trial as such an analgesic adjuvant. Support for this assertion is given below

**Baclofen pharmacology.** The drug baclofen (chemical name) is a GABA derivative. Its mechanisms of action is through the metabotropic GABA-B receptor and is G-protein linked to potassium channels leading to neuronal hyperpolarization. Baclofen is a white powder, practically odorless powder which is manufactured in 10 and 20 mg tablets with typical doses for spasticity of 10-20 TID. It is rapidly absorbed and has half-life of 2-4 hours. 85% of the compound is excreted unchanged in urine.

Sites of action are peripheral, spinal and supraspinal. Selective spinal infusion is utilized to control spasticity. Notable for this discussion, CASL imaging of the brain before and after 21 days of baclofen treatment (20 QID) demonstrated reduced rCBF in the ventral striatum and medial prefrontal cortex and increased rCBF in the lateral OFC, (a region involved in suppressing previously rewarded behavior) and cerebellum. rCBF was also blunted in the insula bilaterally [Franklin et al, 2011].

**Baclofen produces analgesia.** Baclofen produces analgesia by itself as measured in rats and mice in the hot plate, tail flick and acetic acid-induced writhing [Aley and Kulkarni, 1989, 1991; Balerio and Rubio; mult other] In rats with chronically inflamed paws baclofen increased Substance P release raising issues related to acute vs. chronic analgesic benefits of the GABA-B agonists [Malcangio and Bowery, 1994; Galeotti et al 1996]. Baclofen produced analgesia in primates in the formalin test [Sharma et al, 1993]. In chemotherapy-induced neuropathic pain models baclofen produced significant but erratic analgesia [Xiao et al, 2008]. Intrathecal nociceptin antagonized baclofen-induced analgesia in a mouse tail flick assay [Citterio et al, 2000] and baclofen-induced analgesia was absent in GIRK2 knockout mice [Blednov et al] Baclofen administered spinally (intrathecally) produces analgesia in rat thermal pain models that can be antagonized by GABA-B antagonists [Aran and Hammond ]. Whitehead et al [2012] demonstrated peripheral analgesic effects of baclofen in a mouse arthritis model.

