Baclofen's analgesic effects may be acting via the same mechanism by which heterosegmental noxious stimuli produce inhibition (nociceptive inhibition) since such inhibition has been demonstrated to act via GABA-B and mu opioid mechanisms [Tambell et al, 2009]. Consistent with this, analgesia produced by 100 Hz electroacupuncture as involves GABA-B mechanisms [Silva et al]. GABA-B receptor blockade also blocks foot-shock induced "stress-induced" analgesia, but not forced swim stress or psychological stress [Tokuyama et al] although others have observed potentiation of forced swim stress-induced analgesia by baclofen [Houston et al, 1997]. In the spinal substantia gelatinosa activation of GABA-B receptors presynaptically block neurotransmitter release [Yang and Ma] and NK1 receptor expression [Enna et al]. Other sites of action related to pain include the rostral agranular insular cortex [Jasmin et al] and lateral preoptic area [Lim et al]. The supraspinal analgesic effects of baclofen appear to act via adrenergic and opioidergic spinal mechanisms [Jasmin et al; Ignatov and Andreev;] with potentially a cholinergic and GABA-A portion to contribution [Tamayo et al 1988; Zarridast MR and Djavdan M].

In humans, baclofen has had a particular role as an anesthetic for cranial nerve-related neuropathic pains such as trigeminal neuralgia [Knotkova and Pappagallo] . Early anecdotal reports (e.g. Harmer and Larson) suggested it worked for postherpetic neuralgia in facial distributions but not spinal distributions [Terrence et al, 1985]. In humans, the spinal administration of baclofen has also demonstrated short-term analgesic effects on spinal cord injury-related pain and post-stroke pain [Taira et al, 1995]. One presumed mechanism for the action of baclofen on facial pain is the presence of GABA-B receptors on

trigeminal primary afferent neurons whose activation leads to a potentiation of voltage-dependent potassium currents. Baclofen has demonstrated analgesic effects on surgical pain in females [Corli et al]

**Baclofen interacts with opioids synergistically.** Gordon et al (1995) observed potentiation of morphine analgesia on post-operative pain but not of pentazocine-induced (kappa) analgesia. Panerai et al [1985] had previously demonstrated baclofen prolonged the analgesic effect of fentanyl on post-operative pain. Notably, baclofen also potentiates the analgesia produced by clonidine in rat models [Przesmycki et al]

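### Excessive sedation, a secondary outcome, has patient self-assessment as its only named method, and respiratory events and opioid reversal are not named, so the sedation count may be too low

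*Combined protocol and SAP*

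**What the plan says.** All references are to the combined protocol and SAP.

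- **Outcomes (Section 6).** The primary outcome is postoperative opioid consumption. The secondary outcomes are "Incidence of nausea/vomiting; excessive sedation per patient self assessment; any other untoward events".
- **Recording (Section 6).** A separate sentence says that "measures of any other side effects (nausea, excessive sedation) will be recorded for 24 hours". It gives no assessor, scale, schedule or cut-off.
- **Opioid exposure (Section 6).** The plan describes "an attempt to utilize consistent doses of intraoperative opioids other agents across groups", standardized PACU orders, and PCA morphine after PACU discharge. The treating anesthesiologist and PACU staff are blinded.
- **Rationale (Section 2).** One paragraph is headed "Baclofen interacts with opioids synergistically". It cites a study that "observed potentiation of morphine analgesia on post-operative pain" and another on fentanyl.
- **Drug information (Section 8).** Mild sedation is marked as a frequent effect. The Precautions line does not mention giving baclofen with opioids.
- **Run-in and groups (Section 5).** Six open-label patients receive 10 mg so that side effects can be looked at unblinded. Four groups of 20 are then randomized, with patients "receiving either baclofen (10 mg, p.o. x 1) or placebo as a preoperative medication".
- **Analysis (Section 9).** Fisher's exact test is assigned to incidence data.

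**The concern.** The plan gives a drug with a known sedative effect alongside opioids, and makes excessive sedation one of its own outcomes. The one method it names depends on the patient noticing and reporting the state being measured. The patients who matter most for this outcome may be the least able to do so.

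Respiratory depression, oxygen desaturation and use of an opioid-reversal drug are not named anywhere as outcomes. They may be reported as untoward events, but nothing requires that each patient be checked for them. A report of no such events would then be hard to read.

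What is at stake is how far the trial's tolerability results can be trusted. Section 7 foresees a follow-up study with postoperative baclofen for up to 2 weeks, for which these results would be a natural starting point. The opioid-consumption result does not depend on any of this.

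**Working it through.** The plan states no figure on this point, so there is none to reproduce. The check is mostly a reading of the text, with one calculation on respiratory events.

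**1. Is another sedation method named?** There are three candidate places.
- The Section 6 outcome list names self-assessment.
- The Section 6 sentence on 24-hour recording names no method. It does not limit capture to self-report, and it does not establish staff charting.
- The Section 5 run-in names no method.

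Self-assessment is therefore the only stated method.

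**2. Which way would the sedation count err?** Let p be the true proportion with excessive sedation and s the share of true cases that patients report, with s at most 1. Setting false reports aside, the expected reported proportion is s × p, which cannot exceed p. If s is the same in both arms, the reported difference is s × p(baclofen) − s × p(placebo) = s × (true difference), and the ratio of the arms is unchanged. The documents give neither p nor s, so the direction can be argued but the size cannot be calculated.

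**3. Can the run-in fill the gap?** It has n = 6.
- The chance of seeing at least one event is 1 − (1 − p)^6. For an assumed true rate of 5% this is 1 − 0.95^6 = 26.5%; for 10% it is 1 − 0.90^6 = 46.9%.
- With no events in 6, the exact two-sided 95% upper limit is 1 − 0.025^(1/6) = 45.9%.

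The run-in is too small to replace systematic capture, whatever method it uses.

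**4. What would zero respiratory events mean?** The baclofen arms total 2 × 20 = 40 (Section 5). With 0 events in n patients actually checked, the exact two-sided 95% upper limit is 1 − 0.025^(1/n).

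| Patients checked (n) | Upper limit |
|---|---|
| 40 | 1 − 0.025^(1/40) = 8.8% |
| 30 | 1 − 0.025^(1/30) = 11.6% |
| 20 | 1 − 0.025^(1/20) = 16.8% |
| unknown | none can be given |

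The values 30 and 20 are assumed to show the range. This step applies to respiratory events and opioid reversal only. For sedation, the plain reading of Section 6 is that every patient is assessed, so its denominator is not in doubt.

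**The case against.** The strongest reply is that patients are monitored anyway. Care follows local standards, PACU orders are standardized, and the residual category can hold any respiratory event. The dose is a single 10 mg tablet, at the low end of the usual range given in Section 2. The stated purpose is opioid requirements: the hypothesis is that baclofen will "reduce postoperative opioid requirements measured in the PACU and in the first 24 hours following surgery". Most of this stands. It protects patients and keeps the point small. It does not turn clinical monitoring into trial data, because nothing in the plan brings the charted observations into the results.

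A second reply is that the weakness of self-report in heavily sedated patients is not documented in the plan. That is correct. It is clinical reasoning, and the count is therefore said only to be possibly too low.

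Four stronger readings are tempting, and the documents do not support them.

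- **Baclofen raises the risk of opioid respiratory depression.** A reader might infer this from the synergy heading. The evidence cited there concerns analgesia, and no respiratory potentiation is shown.
- **The arms are measured differently.** The design is double-blind, and nothing in the text points to differential recording.
- **Sedation has no known denominator.** Section 6 reads as recording it for all patients.
- **The concern ends with the PACU stay.** A reader might infer this from "It is rapidly absorbed and has half-life of 2-4 hours". But Section 2 also says that 85% is excreted unchanged in urine and that toxicity is more common in advanced nephropathy, while Section 4 has no renal exclusion in a kidney-stone population. Timing figures built on that half-life could mislead.

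**Conclusion.** The concern holds in a limited form: safety capture is incomplete. Excessive sedation rests on a single named method that may miss the most affected patients, and respiratory events and opioid reversal are not collected systematically. The likely error is an undercount of sedation, of unknown size. For respiratory events, a finding of none could be compatible with a rate of up to 8.8% at best, and with no stated limit if the number checked is not recorded.

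This rests on two assumptions: that heavily sedated patients under-report, and that PACU and ward charts already hold a usable sedation score. The documents confirm neither.

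The primary outcome and its analysis do not change. No excess risk and no bias between arms is shown. The change is optional, but it is cheap and would make a secondary outcome easier to interpret. The missing opioid line in Section 8 is a lesser matter; the consent pages are not available, so risk wording there cannot be checked.

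**What to change.** In Section 6:

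- Keep self-assessed excessive sedation as it is, with the Fisher's exact test planned in Section 9.
- Add the sedation score that staff already chart in PACU and on the ward, from PACU arrival to 24 hours after surgery. Starting at PACU arrival leaves out the anaesthetic period, when the score cannot be interpreted. Name the scale, and fix the cut-off for excessive sedation before unblinding.
- From the same charts and over the same period, record use of an opioid-reversal drug, and desaturation or respiratory depression at a threshold fixed in advance.

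In Section 9, state that the chart-based items are reported by arm as counts over the number of patients charted for that item, with exact 95% intervals and no test. This leaves the planned tests as they are.

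A line on opioid co-administration under Precautions in Section 8 is optional.

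The cost is slightly more chart abstraction, a few data fields and a few table rows. No new procedure or extra staff is needed if the charts hold these items. Some items may not be charted for every patient, which is why the charted number must be reported, and the results will describe rates rather than compare arms formally.
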